5.4. Definition of adherence

Adherence to allocated intervention will be monitored by recording the administration of each of the four trial interventions and reasons why any of the trial interventions were not given. Blood banks will also monitor receipt of unused trial interventions upon return of the transport boxes.

We will define adherence, in the crystalloid arm of the trial, as the administration of at least one bolus of fluid. In the PHBP arm, adherence is defined as the administration of at least one unit of PRBC and one unit of LyoPlas. Non-adherence will be defined as the failure to administer at least one bolus of fluid in the crystalloid arm or the failure to administer at least one unit of PRBC and one unit of LyoPlas in the PHBP arm without clinical justification (e.g. deemed not to be needed clinically, or, patient arrives at ED before the second bolus can be administered, etc.).

The 'per protocol' population will include only those participants considered adherent to allocated intervention as described above.

5.5. Handling protocol deviations

A protocol deviation is defined as a failure to adhere to the protocol such as errors in applying the inclusion/exclusion criteria, the incorrect intervention being given, incorrect data being collected or measured, follow-up visits outside the visit window or missed follow-up visits. We will apply a strict definition of the ITT principle and will include all participants as per the ITT population described in section 5.3 in the analysis in some form, regardless of deviation from the protocol.⁶ This does not include those participants who have specifically withdrawn consent for the use of their data in the first instance; however these outcomes will be explored as per other missing responses.

5.6. Unblinding
Not applicable, RePHILL is an open-label study
6. Trial population
6.1. Recruitment
A flow diagram (as recommended by CONSORT ⁷) will be produced to describe the participant flow through each stage of the trial. This will include information on the number (with reasons) of losses to follow-up (drop-outs and withdrawals) over the course of the trial. A template for reporting this is given in Appendix D1.
6.2. Baseline characteristics
The trial population will be tabulated as per Appendices D2, D2a and D2b. Categorical data will be summarised by number of participants, counts and percentages. Continuous data will be summarised by the number of participants, mean and standard deviation if deemed to be normally distributed or number of participants, median and interquartile range if data appear skewed, and ranges if appropriate. Tests of statistical significance will not be undertaken, nor confidence intervals presented. ⁸
7. Interventions
7.1. Description of the interventions
Not applicable
7.2. Adherence to allocated intervention
A cross-tabulation of allocated intervention by the adherence categories stated in section 5.4 will be produced (proportions and percentages). A template for reporting adherence is given in Appendix D4.
8. Protocol deviations
Frequencies and percentages by group will be tabulated for the protocol deviations as per Appendix D5.
9. Analysis methods

9.1. Covariate adjustment

In the first instance, intervention effects between groups for all outcomes will be adjusted for IDS (stratification variable; see section 4.6) as a fixed effect (this will be the primary analysis). A secondary analysis adjusting for IDS and the following prognostic variables (age, lactate, cardiac arrest and Glasgow Comma Score (GCS) at randomisation) as fixed effects will also be undertaken for the primary outcome measure (and the individual components).

For binary outcomes, if the log-binomial model fails to converge, a Poisson regression model with robust standard errors will be used to estimate the same parameters.⁹ If this also fails to converge, unadjusted estimates will be produced from the log-binomial model. It will be made clear in the final report why this occurred (e.g. not possible due to low event rate/lack of model convergence).

Longitudinal secondary outcomes (e.g. vital signs, venous lactate concentration, etc.) will also be adjusted for their baseline values.

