4.6. Randomisation

Participants will be randomised at the level of the individual in a 1:1 ratio to either PHBP (Lyophilised Plasma LyoPlas N-w (LyoPlas) and PRBC) resuscitation or crystalloid (0.9% sodium chloride [normal saline]) resuscitation.

Randomisation will be performed centrally at the Birmingham Clinical Trials Unit (BCTU) using stratification by intervention delivery site (IDS) to account for variation in trauma care and type of trauma between delivery sites.

In the RePHILL trial, the blood banks will maintain a constant supply of randomised trial interventions to the Pre-Hospital Emergency Medical (PHEM) team. The blood bank will obtain the randomised allocations via a secure online system at the BCTU.

Blood banks will be supplied with pre-printed 'treatment box number' labels. A registered user at the blood bank will request a treatment allocation from the BCTU and will receive a treatment box number and treatment arm allocation. The allocated trial intervention will be packed into transport boxes affixing the correct labels. Transport boxes will be issued as a pair, one marked red and one marked yellow per single randomised allocation. The packed, sealed transport

boxes will be dispatched to the PHEM base using an established courier service as required

On-scene, the PHEM doctor will assess the potential participant's vital signs on scene and confirm if eligible for entry into the RePHILL trial. If they fulfil the eligibility criteria for the trial, the randomised treatment will be given. Participants are considered randomised into the trial when the PHEM team open the first transport box containing the allocated trial intervention.

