5.3. Analysis populations

All primary analyses (primary and secondary outcomes including safety outcomes) will be based on the intention-to-treat (ITT) principle. Participants will be analysed in the intervention group to which they were randomised, and all participants shall be included whether or not they received the allocated intervention. This is to avoid any potential bias in the analysis.

A per protocol analysis will be carried out as a sensitivity analysis and will only be performed for the primary outcome. Adherence and the per protocol group are defined in section 5.4.

Further details on the sensitivity analyses are given in section 9.10.

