9.8. Safety data

The number and percentage of participants experiencing any adverse events, serious adverse events (SAEs) and suspected unexpected serious adverse reactions (SUSARs) will be presented by intervention group. Statistical significance will be determined by a chi-squared test. The total number of SAEs in each group will also be given along with a descriptive table of the details of the events. A template for reporting this data is given in Appendix D8.

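### Section 9.8 tests adverse events and listed complications with an unstratified chi-squared test, although 9.1 adjusts all outcomes for delivery site: a minor inconsistency in a valid but sometimes conservative test

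*SAP*

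**What the plan says.** Section 4.6 randomises 1:1, "using stratification by intervention delivery site (IDS) to account for variation in trauma care and type of trauma between delivery sites". Section 9.1 sets the general rule that, in the first instance, "intervention effects between groups for all outcomes will be adjusted for IDS", as a fixed effect, and calls this the primary analysis. Section 5.3 places safety within the scope of outcomes: "All primary analyses (primary and secondary outcomes including safety outcomes) will be based on the intention-to-treat (ITT) principle".

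Section 9.8 then sets the comparison for participants with any adverse event, any SAE or any SUSAR: "Statistical significance will be determined by a chi-squared test". It names no stratification and no site term. Its reporting template, Appendix D8, has counts, percentages and p-values for transfusion-related lung injury, thromboembolism and its subtypes, infection and its subtypes, SAEs and SUSARs. It has no column for an adjusted effect.

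Other outcomes that bear on harm take a different route. Section 9.6 analyses binary secondary outcomes as the primary outcome is analysed, that is, by a log-binomial model adjusted for IDS. Appendix D7 accordingly lists adjusted effects for ARDS, transfusion-related complications, episode mortality, and 3-hour and 30-day mortality.

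For binary outcomes, section 9.1 also gives an ordered fallback. If the log-binomial model fails, robust Poisson regression is used. After that: "If this also fails to converge, unadjusted estimates will be produced from the log-binomial model". The rule adds: "It will be made clear in the final report why this occurred".

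**The concern.** Section 9.1 makes a statement about all outcomes, section 5.3 includes safety among them, and section 9.8 does something else without saying that it is an exception. Two analysts following the SAP could report different safety p-values for the same row, each with support in the text. Closely related harms are also split without a stated reason: transfusion-related complications are adjusted for site in D7, while transfusion-related lung injury is tested without site in D8.

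There is a statistical side too. When randomisation is balanced within sites and event rates differ between sites, an unstratified test uses a variance that includes the between-site component, although the design has removed it from the treatment comparison. The test then rejects less often than its nominal 5%, and it loses some power. In a harm comparison, that makes a real excess somewhat easier to miss.

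**Working it through.** **Inputs from the SAP.** Total 490 participants, 1:1 (4.6, 4.7), so 245 per arm; four delivery sites (Appendix D2); two-sided 5% level (5.1). The SAP states no power for any safety comparison. Its own design figure, for the primary outcome, reproduces: 20% versus 10% with 80% power and a continuity correction gives 219 per group, with exact Fisher power of 81.2%. Then 438/0.9 = 487 against the stated 490.

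**Inputs assumed.** Site-specific safety rates, site shares and the size of any harm effect. The documents give none of these.

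**Step 1: how far the unstratified variance is too large.** With equal sites and site rates p_k of mean p̄, the ratio of the within-site standard error to the total standard error is r = sqrt[ mean of p_k(1−p_k) / (p̄(1−p̄)) ].

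| Assumed site rates | within / total variance | r |
|---|---|---|
| 10/15/25/30% | 0.15375 / 0.16000 | 0.98 |
| 5/10/20/50% | 0.13688 / 0.16734 | 0.90 |
| 5/5/30/60% | 0.13625 / 0.18750 | 0.85 |
| 1/2/4/6% (uncommon events) | 0.03107 / 0.03144 | 0.994 |

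**Step 2: true size of the chi-squared test.** Under no effect its z statistic has standard deviation of about r, so the size is about 2[1−Φ(1.96/r)]. For the first three rows this gives about 4.6%, 3.0% and 2.2%; simulation below gives 4.7%, 3.1% and 2.3%. The test is conservative and its error rate is not inflated.

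**Step 3: power.** Simulation, 245 per arm, four equal sites, PHBP:crystalloid relative risk 1.5, chi-squared versus Cochran-Mantel-Haenszel (CMH) stratified by site:

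| Assumed site rates | chi-squared | CMH | Loss |
|---|---|---|---|
| 10/15/25/30% | 73% | 75% | 2 points |
| 5/10/20/50% | 79% | 87% | 8 points |
| 5/5/30/60% | 91% | 97% | 6 points |

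With equal site rates the two tests agree.

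**Step 4: a wider grid.** A second simulation used 490 participants, base control rates of 5% to 30%, odds ratios of 1.8 and 2.2, equal or 40/30/20/10 site shares, and 100,000 replicates per setting. The power gained by stratifying was:

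- no site differences: −0.2 to +0.1 points;
- moderate differences (log-odds SD 0.5, for example site rates of 11% to 33%): 0.2 to 1.3 points;
- very large differences (log-odds SD 1.0, for example 10% to 62%): 1.8 to 6.5 points.

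The size of the chi-squared test in this grid lay between 3.1% and 5.0%.

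**Step 5: combined range.** About 0 to 2 points for no to moderate differences between sites, and about 2 to 8 points for very large ones.

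**The case against.** The best defence is that section 9.1 governs estimated effects, while section 9.8 and Appendix D8 plan only counts and a p-value, so the specific safety section can be read as an exception to the general rule. That reading is possible, but the SAP does not state it. The opening qualifier of 9.1, that the rule holds in the first instance, does not supply it either, since it introduces the contrast with the secondary analysis that adds prognostic variables. The defence shows that the conflict is thin, not that it is absent.

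Three stronger readings are tempting, and the documents do not support them.

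- *Every safety outcome ignores the strata.* It does not. Secondary objective VII concerns transfusion-related complications, particularly ARDS. Both, with mortality, are adjusted for site under 9.6 and D7.
- *The last fallback in 9.1 contradicts 9.1.* It does not. It is part of the same section, is reached only after two adjusted models have failed, and must be explained in the report. Nothing in the SAP shows how often it would be reached or what it would cost.
- *The trial materially loses power to detect harm.* The losses of 6 to 8 points need rates that differ 10- to 12-fold between four services (5% against 50% or 60%). In the most extreme case, a relative risk of 1.5 takes a site from 60% to 90%. The SAP offers no figures for such differences. If the rarer D8 rows run at something like 1% to 6%, r is 0.994 and stratifying gains almost nothing.

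It also stands that the unstratified test remains valid, and that it touches neither the primary outcome nor any outcome listed in D7.

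**Conclusion.** The inconsistency is real and limited to the adverse event, SAE, SUSAR and complication rows of 9.8 and D8. Section 9.8 names the chi-squared test for the first three. That it also covers the complication rows follows because D8 is the template for 9.8 and no other test is given for them. The consequence is a conservative test, with a size between about 2.3% and 5% in the settings examined. The range of power loss above rests wholly on assumed site rates, site shares and effect sizes. Severity is minor: the reason to change is mainly that the plan should name one analysis, and the design already provides the strata for it.

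**What to change.** In section 9.8 and Appendix D8, replace the chi-squared test with a Cochran-Mantel-Haenszel test stratified by IDS. This aligns 9.8 with 9.1. An exact version may be used for sparse rows, with a note that exact tests are themselves conservative. Merely declaring 9.8 an exception to 9.1 would remove the ambiguity but leave the conservative test in place.

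As an optional improvement, and not to correct a contradiction, the last fallback in 9.1 could be a Mantel-Haenszel relative risk and risk difference stratified by IDS, with 95% confidence intervals, in place of the unadjusted log-binomial estimate. These need no iterative fitting and keep the randomisation strata.

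The cost is a few lines of SAP text and a standard option in the software already named (SAS). No new data are needed. Where site rates do not differ, the change in power is essentially nil.

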9.3. Handling missing data

In the first instance, analysis will be completed on received data only with every effort made to follow-up participants to minimise any potential for bias. To examine the possible impact of missing data on the results, and to make sure we are complying with the intention-to-treat principle, sensitivity analysis will be performed on the primary outcome measure.¹⁰ See section 9.10 for further details regarding planned sensitivity analyses.

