9.4. Data manipulations

The Trial Statistician will derive all responses from the raw data recorded in the database.

Age

Lactate clearance, expressed as a percentage per hour (%/h), is calculated using the formula:

A normal lactate is taken to be ≤ 2.2 mmol/L. Achieving $\geq 20\%$ per hour lactate clearance is defined as follows in participants whose:

- a) is > 2.2 mmol/L and whose demonstrates lactate clearance of $\geq 20\%$ per hour; or
- b) is > 2.2 mmol/L, but whose is ≤ 2.2 mmol/L, regardless of the magnitude of the change; or
- c) and are both ≤ 2.2 mmol/L, regardless of the magnitude and direction of any difference

All the above will be counted as participants achieving $\geq 20\%$ per hour lactate clearance

The above can be summarised in the following table:

(mmol/L)	(mmol/L)	Required lactate clearance
> 2.2	> 2.2	$\geq 20\%$ per hour
> 2.2	≤ 2.2	Not applicable
≤ 2.2	≤ 2.2	Not applicable

Achieving $< 20\%$ per hour lactate clearance is defined as follows in participants:

- a) Whose is > 2.2 mmol/L and whose demonstrates lactate clearance of $< 20\%$ per hour; or
- b) Who die prior to interval sampling (e.g. before the measurement is taken at) For this we require the date and time of death from the exit form to determine if the participant died within two hours and 30 minutes of randomisation

The table below summarises what is considered an event (failure to achieve lactate clearance):

(mmol/L)	(mmol/L)	Lactate clearance $< 20\%$ per hour	Lactate clearance $\geq 20\%$ per hour
> 2.2	> 2.2	Failure to clear (event)	Achieves clearance
> 2.2	≤ 2.2	Achieves clearance	Achieves clearance
≤ 2.2	≤ 2.2	Achieves clearance	Achieves clearance
Dies prior to interval sampling and within 2.5 hours of randomisation		Failure to clear (event)	

There are instances where the lactate value is too high for a value to be reported, i.e. the value is out of range (OOR) of the detection level of the test. In these cases, the lactate measurement is recorded on the database as "too high to be recorded". In these instances, at database lock prior to analysis, a review of these lactate values will be undertaken independently by two statisticians blind to treatment allocation to assess whether the participant cleared their lactate or not. For example, if randomisation lactate is OOR, but the 2-hour randomisation lactate is

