9.5. Analysis methods - primary outcome(s)

A template for reporting the primary outcome is given in Appendix D6.

The primary outcome is a composite measure of episode mortality or failure to clear lactate and is measured as a binary outcome. Participants clearing less than 20% per hour of their lactate between randomisation and 2 hours after randomisation or dying between time of injury/recruitment and discharge to non-acute care will be defined as experiencing the primary outcome. The primary outcome measure will be summarised as the number of participants experiencing the primary outcome with percentages.

Adjusted relative risks (adjusted for IDS) along with 95% confidence intervals will be estimated using a log-binomial regression model. Statistical significance of the treatment group parameter

will be determined from the p-value generated by the model. The absolute risk difference along with 95% confidence intervals will be estimated using a binomial regression model with identity link. As this is a composite endpoint, the primary outcome will also be reported in accordance with the recommendations of Ferreira-Gonzalez et al¹¹, with the qualifying event for the primary outcome presented using the template in Appendix D6a.

See section 9.1 for details on covariate adjustment and model convergence.

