Appendix D1: CONSORT flow diagram

Appendix D2: Baseline characteristics

		PHBP (n=xxx)	Crystalloid (n=xxx)	Overall (n=xxx)
Stratification variable				
Intervention Delivery Site	Midlands Air Ambulance (MAA)	n (%)	n (%)	n (%)
	MAGPAS	n (%)	n (%)	n (%)
	The Air Ambulance Service (TAAS)	n (%)	n (%)	n (%)
	East Anglian Air Ambulance (EAAA)	n (%)	n (%)	n (%)
Demographic and other baseline variables				
Gender	Male	n (%)	n (%)	n (%)
	Female	n (%)	n (%)	n (%)
	Missing	n (%)	n (%)	n (%)
Age, years	Mean (SD)			
	Missing	n (%)	n (%)	n (%)
Ethnic Group, n (%)	White (British)	n (%)	n (%)	n (%)
	White (Irish)	n (%)	n (%)	n (%)
	White (Other)	n (%)	n (%)	n (%)
	Black (Caribbean)	n (%)	n (%)	n (%)
	Missing	n (%)	n (%)	n (%)
Capillary lactate concentration (mmol/L)	Mean (SD)			
	Missing	n (%)	n (%)	n (%)
Mechanism of injury(ies) (More than one can apply)	Fall from <2m	n (%)	n (%)	n (%)
	Fall from ≥2m	n (%)	n (%)	n (%)
	Inhalation	n (%)	n (%)	n (%)
	Road traffic accident	n (%)	n (%)	n (%)
	Burn injury	n (%)	n (%)	n (%)
	Head Injury	n (%)	n (%)	n (%)
	Gunshot wound	n (%)	n (%)	n (%)
	Stabbing	n (%)	n (%)	n (%)
	Other	n (%)	n (%)	n (%)
	Missing	n (%)	n (%)	n (%)
Acute Brain Injury	Yes	n (%)	n (%)	n (%)
	No	n (%)	n (%)	n (%)
	Missing	n (%)	n (%)	n (%)
Mode of transport	Air	n (%)	n (%)	n (%)
	Ground	n (%)	n (%)	n (%)
	Missing	n (%)	n (%)	n (%)
Haemorrhage	Compressible	n (%)	n (%)	n (%)
	Non-compressible	n (%)	n (%)	n (%)
	Missing	n (%)	n (%)	n (%)
Category of injury	Blunt	n (%)	n (%)	n (%)
	Penetrating	n (%)	n (%)	n (%)
	Crush	n (%)	n (%)	n (%)
	Missing	n (%)	n (%)	n (%)
Tranexamic Acid				
Has the participant been given a tranexamic acid bolus?	Yes	n (%)	n (%)	n (%)
	No	n (%)	n (%)	n (%)
	Missing	n (%)	n (%)	n (%)
On-scene Vital Signs				
Systolic Blood Pressure ¹ (mmHg)	Zero	n (%)	n (%)	n (%)
	Non-zero	n (%)	n (%)	n (%)
	Missing	n (%)	n (%)	n (%)

		Mean (SD)			
Diastolic Blood Pressure ¹ (mmHg)	Zero	n (%)	n (%)	n (%)	
	Non-zero	n (%)	n (%)	n (%)	
	Missing	n (%)	n (%)	n (%)	
		Mean (SD)			
Heart Rate ¹ (bpm)	Zero	n (%)	n (%)	n (%)	
	Non-zero	n (%)	n (%)	n (%)	
	Missing	n (%)	n (%)	n (%)	
		Mean (SD)			
Respiratory Rate ¹ (/min)	Zero	n (%)	n (%)	n (%)	
	Non-zero	n (%)	n (%)	n (%)	
	Missing	n (%)	n (%)	n (%)	
		Mean (SD)			
Cardiac Arrest ²	Yes	n (%)	n (%)	n (%)	
	No	n (%)	n (%)	n (%)	
	Missing	n (%)	n (%)	n (%)	
Capillary oxygen saturation (SpO ₂) (%)		Mean (SD)			
GCS		Missing	n (%)	n (%)	n (%)
		Median (IQR)			
Suspected at time of injury	Missing	n (%)	n (%)	n (%)	

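### The covariate-adjusted and baseline-adjusted models have no rule for an unrecorded baseline value, so participants with a known outcome drop out of them

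*SAP*

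**What the plan says.** All references are to the SAP.

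- **Section 9.1.** The primary analysis adjusts for IDS only. It is followed by "A secondary analysis adjusting for IDS and the following prognostic variables (age, lactate, cardiac arrest and Glasgow Comma Score (GCS) at randomisation) as fixed effects", covering the composite and each component. Section 9.10 lists the same model for the composite as a sensitivity analysis. Longitudinal secondary outcomes "will also be adjusted for their baseline values", and section 9.6 repeats this for continuous outcomes.
- **Section 9.3.** "In the first instance, analysis will be completed on received data only". No rule is given for a missing covariate.
- **Section 9.5.** A participant "dying between time of injury/recruitment and discharge to non-acute care will be defined as experiencing the primary outcome", so a death counts as an event whatever lactate data exist.
- **Section 9.10.** Multiple imputation is aimed at missing responses. Its imputation model lists age, randomisation lactate, cardiac arrest and GCS. It does not say that missing values of these are filled in, or that the four-covariate model is fitted to the imputed datasets. Sensitivity analyses are confined to the primary outcome.
- **Section 5.3.** Primary and secondary outcomes are to be analysed by intention to treat, with every randomised participant included.
- **Appendix D2.** The template has a row for missing values under "Capillary lactate concentration (mmol/L", and likewise for age, cardiac arrest, GCS, blood pressure and heart rate.

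**The concern.** A regression fitted to received data uses only records in which every covariate has a value. Someone who died with no randomisation lactate, GCS or age on file is an event in the IDS-only model but is absent from the four-covariate model. A participant with a blood pressure at ED arrival but none on scene is likewise lost from the main comparison for secondary objective I, where no sensitivity analysis stands behind it.

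The four-covariate model is there to show whether the primary result survives adjustment for prognosis. If it is fitted to a different set of people, a difference between the two results cannot be put down to adjustment. Outcomes that were collected are also discarded, which costs precision and sits badly with section 5.3.

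**Working it through.** **1. The plan's own figures, used as the base case.** Section 4.7 gives 20% vs 10%, 80% power and two-sided 5%. The two-proportion formula gives [1.960·√(2·0.15·0.85) + 0.842·√(0.16+0.09)]²/0.10² = 199 per group, or 219 with continuity correction, as stated. 438/0.9 = 487, against the stated 490. For the revised rates, 490 × 0.9 / 2 ≈ 220 per group, and exact Fisher power at 71.7% vs 58.3% is 81.8%, against the stated 80%. The base case is therefore 220 per group with 0.717 × 220 ≈ 158 and 0.583 × 220 ≈ 128 events, RR = 128/158 = 0.810. None of these figures concerns missing covariates; the SAP gives none.

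**2. Who is in which model under the received-data rule.**

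| Participant | IDS-only composite | Four-covariate composite | IDS-only mortality | Four-covariate mortality |
|---|---|---|---|---|
| Death, randomisation lactate unrecorded | in, as event | out | in | out |
| Survivor, randomisation lactate unrecorded | usually out (clearance cannot be derived) | out | in | out |
| Lactates known; GCS, age or arrest status unrecorded | in | out | in | out |

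For lactate, those lost from the composite only on adjustment are thus mainly deaths, all of them events. For mortality, both deaths and survivors with known outcomes are lost. This concerns values never recorded; lactates above the assay range are a separate case.

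**3. How far the two composite sets could differ (assumed losses).** Remove deaths from the base case, before any adjustment:

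- 22 deaths (5% of 440), split 11/11: RR = (117/209)/(147/209) = 0.796; events lost 22/286 = 7.7%.
- 44 deaths (10%), split 22/22: RR = (106/198)/(136/198) = 0.779; events lost 44/286 = 15.4%.
- 22 deaths, split 14 standard care / 8 PHBP: RR = (120/212)/(144/206) = 0.810, no shift.

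For scale, the base-case 95% CI uses SE(log RR) = √(1/128 − 1/220 + 1/158 − 1/220) = 0.071, giving about 0.70 to 0.93.

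**4. Vital signs (assumed missingness).** Losing 10% to 30% of participants widens the interval by 1/√0.9 = 1.05 to 1/√0.7 = 1.20. Filling in the baseline recovers part of this, not all.

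**5. What a fill-in rule does.** Simulation with about 10% missing, more often in sicker participants (both assumed):

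- Episode mortality: SE 0.120 complete-case, 0.110 with pooled mean plus indicator, a fall of 0.010/0.120 = 8%.
- Vital signs: SE 1.375 to 1.328, a fall of 0.047/1.375 = 3%.
- Composite with missing lactate: RR 0.837 with full data, 0.835 complete-case, 0.848 with the indicator.

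A second simulation of the composite (490 participants, true RR 0.82, about 10% missing lactate, survivors' composite then missing) gave 0.821 complete-case and 0.831 with the indicator. The log-binomial model failed or reached its boundary in every run with the indicator, against 62% of complete-case runs. The reason is in the table: participants with missing lactate who still have a composite value are nearly all events, so the indicator marks a group with an event rate near 100%.

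**The case against.** Much of the case on the other side stands.

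- The primary analysis is IDS-only and uses none of these covariates. The four-covariate model is secondary, and no decision rule hangs on it.
- The SAP nowhere says that these participants are dropped. This follows from the received-data rule together with the lack of a covariate rule.
- Section 9.10 already names the four covariates in an imputation model, so a clarification there could cover the composite. As written, it is aimed at responses, and a death's composite response is known.
- Nearly every variable in Appendix D2 has a row for missing values, so the template shows only that missingness is possible.
- Vital signs are assessed on scene for eligibility, and readings of zero are recorded as zero. Participants in arrest with recorded zeros therefore stay in the models. On-scene deaths have no ED-arrival value to lose.

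A reader might go further and infer that the adjusted relative risk is biased. The documents do not support that. Baseline values are meant to precede box opening, so their absence should not depend on arm, although the trial is open-label. Dropping everyone with a missing baseline value then leaves a randomised comparison in a subset. A simulation that removed only events (true RR 0.813) did move the adjusted RR, to 0.805 with 5% removed and 0.790 with 11%. But for lactate the survivors without a value have usually left as well, so that is not the full picture. A spurious effect under no true difference needs unequal loss by arm: at 65% in both arms, losing deaths equal to 10% of standard care and 5% of PHBP gives (0.60/0.95)/(0.55/0.90) = 1.03. Nothing in the SAP points to such an imbalance.

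**Conclusion.** The point holds as one of precision, population and interpretability. Participants with known outcomes leave the four-covariate and baseline-adjusted models whenever a baseline value is unrecorded. This conflicts with section 5.3, and nothing in section 9.10 clearly restores them. The IDS-only and adjusted results then rest on different people.

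The size cannot be fixed from the SAP. Under the assumed losses, the crude RR differs between the two composite sets by 0 to about 0.03, small against an interval of roughly 0.70 to 0.93. That is a difference between sets, not a demonstrated bias. The standard-error gains from filling in (about 8% for mortality, 3% for vital signs) rest on an assumed 10% missingness.

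It would be wrong to infer that the primary result is compromised. It would also be wrong to treat a missing-value indicator as unbiased everywhere: for missing lactate on the composite it pulled the estimate slightly towards the null.

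**What to change.** Add a missing-covariate rule to sections 9.1 and 9.3, in two parts.

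1. **Episode mortality, vital signs and other baseline-adjusted continuous outcomes.** Keep every participant with an outcome. Replace a missing baseline covariate with its mean over both arms pooled, and add a missing-value indicator.
2. **Composite and lactate clearance.** Do not use the indicator for lactate. In section 9.10, state that missing covariates are imputed jointly with the outcome components in the MCMC model already planned, and that the four-covariate model is fitted to those datasets and combined by Rubin's rules. The listed imputation variables do not name the allocated group; say whether it is included or imputation is run by arm.

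In Appendices D6 and D7, report the number of participants and, for binary outcomes, events in each model, so that any difference between IDS-only and adjusted results can be read against the sets used.

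The cost is a few sentences of SAP text and a slightly wider use of an imputation already planned. The downside of part 1 is slightly less covariate information for the filled-in participants. No new data are needed.
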